1.0 Study Summary

Study Title	Utilization of Low Level Laser Therapy (LLLT) for Radiation-Induced Dermatitis in Patients with Head and Neck Squamous Cell Carcinoma (HNSCC)
Study Design	Single-arm, Phase I/II
Primary Objective/Endpoint	
Assess the safety and efficacy of low level laser therapy (LLLT) in mitigating radiation-induced dermatitis in patients undergoing radiation therapy for head and neck squamous cell carcinoma (HNSCC)
 
Endpoint: Documented Grade 3 or higher Adverse Events as per CTCAE v4.0

Secondary Objective(s)/Endpoints	
assessment of patient-reported quality of life data, pain parameters and dermatologic quality of life responses
 
Endpoints:
 
 • quality of life data measured using the University of Washington Quality of Life Questionnaire (UW-QOL) • pain parameters assessed using Brief Pain Inventory (BPI) • dermatologic quality of life responses measured using the Dermatology Life Quality Index (DLQI)
Research Intervention(s)/Investigational Agent(s)	THOR Laser system
IND/IDE #	N/A
Study Population	patients with histologically proven squamous cell carcinoma of the oral cavity, oropharynx, hypopharynx or larynx who are candidates for either definitive or adjuvant therapy consisting of a chemotherapy regimen and concurrent radiation therap
Sample Size	75 planned
Study Duration for individual participants	15 months

2.0 Objectives

- 2.1 The study aims to assess the safety and efficacy of the utilization of low level laser therapy to mitigate radiation-induced dermatitis in patients undergoing definitive or adjuvant radiation therapy with head and neck squamous cell carcinoma.
- 2.2 The hypothesis is that low level laser therapy given prior to and during the course of treatment will decrease the rate of grade III dermatitis, a common finding seen in patients undergoing radiation therapy with head and neck squamous cell carcinoma. An additional goal of low level laser therapy is to increase wound healing.

3.0 Background

3.1 There are approximately 43,000 cases of head and neck squamous cell carcinoma (HNSCC) diagnosed annually in the United States of which approximately two-thirds will present with locally-advanced disease (Stage III or IV). For these patients, traditional treatment options including surgical resection and adjuvant radiotherapy have been largely supplanted by non-operative approaches. The success of non-operative approaches has been made possible through both refinement of radiotherapy (RT) techniques as well as an increased understanding of the biology of the disease and the subsequent introduction of targeted agents including cetuximab, an inhibitor of the epidermal growth factor (EGFR) (Kabolizadeh et al, 2012).

Much has been learned about the biology of HNSCC including the role of EGFR. This receptor is expressed at high levels in the majority of HNSCC. Furthermore, pre-clinical data indicate that it is intimately associated with the malignant phenotype of HNSCC. EGFR activation in response to its ligand results in phosphorylation of its intracytoplasmic tyrosine kinase domain, leading to a cascade of signal transduction within the cell and ultimately alterations in DNA synthesis, cell proliferation, anti-apoptosis, and transcription of growth factors such as pro-angiogenic molecules. Blockade of this pathway serves as an effective anti-neoplastic as well as radiosensitization strategy.

The anti-neoplastic properties and radiosensitization of EGFR blockade was proven in a landmark randomized trial in patients with locally-advanced, non-operative HNSCC in which patients were randomized to RT alone or RT with weekly cetuximab (Bonner JA, et al., 2010). The investigators found that locoregional control and survival were significantly improved with cetuximab. Specifically, the 3-year rate for freedom from local-regional progression and overall survival were 47% and 55% for RT with cetuximab compared with 34% and 45% for RT alone. The relative reduction in the risk of local-regional progression and death were 32% ($p=0.005$) and 26% ($p=0.03$), respectively (Bonner JA, et al., 2010). Interestingly, improved outcomes were associated with the

development a drug-induced acne-like rash, a common side effect of this class of medications.

In this respect, cetuximab appears to have a different toxicity profile than that of traditional chemotherapy such as cisplatin. The most commonly reported side effect is the development of skin reactions including macular, papular, and pustular rashes, xerosis, fissures, telangiectasias, and hyperpigmentation of the hair and nails (Bernier et al., 2008). The most frequent of these reactions is an acne-like rash that predominately appears in areas rich in sebaceous glands. The acne-like rash comprises itchy erythematous follicular papules that evolve into pustules. Other presentations include diffuse erythema with follicular papulopustules and telangiectasia, a seborrhoeic dermatitis-like rash or, occasionally, an edematous facial erythema. In the absence of radiation, the acne-like rash can be seen within a few days of the initiation of treatment and peaks 2–3 weeks after starting therapy (Bernier et al., 2008).

The effect on the skin during the combination of cetuximab and radiation is of considerable interest, as it might require special care to reduce symptoms and severity. It appears that radiation may delay the onset of the cetuximab-induced rash as it typically appears within irradiated fields 3–5 weeks after initiation of treatment (Bernier et al., 2008). There appears to be no obvious relationship between the severity of cetuximab-associated acne-like rash outside irradiated fields and the severity of radiation dermatitis. The aforementioned Phase III trial (Bonner JA et al., 2010) revealed no statistically significantly increase in the incidence or severity of radiation dermatitis compared with radiotherapy alone. The incidence of grade 3 radiation dermatitis was 18% with RT alone and 23% with RT with cetuximab ($p = 0.27$). There was a slight increase in the median duration of radiation dermatitis in the cetuximab arm (11.1 weeks) compared with the RT-alone arm (9.4 weeks).

While the majority of skin reactions seen with cetuximab are grade 1 or 2 (80%), there is certainly an effect on quality of life (QoL) as well as treatment continuity. A survey of EGFR inhibitor use by oncologists found that 76% of clinicians interrupted treatment due to skin toxicity and 32% discontinued therapy altogether (Boone et al., 2006). However, its prevalence presents an opportunity to explore novel modes of symptom reduction as well as to assess modalities that may improve pain and patient-reported quality of life (PR-QoL). Currently, the most utilized treatments include anti-inflammatory agents, antibiotics, antihistamines, and saline compresses (Bernier et al., 2008). A potential novel strategy to influence both the cetuximab as well as radiation-induced dermatitis is the implementation of low level laser light therapy (LLLT).

3.2 LLLT is potentially effective in wound healing by producing an anti-inflammatory response by promoting cellular metabolism and increasing circulation and lymphatic flow. The mechanism of action may be related to a decrease in interstitial edema and an increase in the healing

process. Its clinical utility in reducing oral mucositis was assessed prospectively and was recently discussed in a Cochrane review (Clarkson et al., 2010; Guatuum AP et al., 2012; Migliorati et al., 2013). Here, LLLT showed a reduction in severe mucositis when compared with the sham procedure (risk ratio: 5.28, 95% confidence interval: 2.30 to 12.13). While these studies support an improvement in oral mucositis with LLLT, the clinical experience addressing an improvement in cetuximab-induced rashes and radiation-dermatitis is limited. An Italian case series (Gobbo et al., 2011) reported that in 4 patients with metastatic colorectal cancer and two patients with HNSCC, LLLT reduced cetuximab-related skin toxicities. Here, patients were treated with two 8-minute long consecutive sessions/day over a 4-day treatment. Patients were evaluated weekly for up to 3 weeks and after 180 days. Follow-up evaluations including a questionnaire about the onset and progression of the acneiform rash and visual analog scales were reported. The authors reported that after the fourth session of LLLT, the patients showed a decrease in both cetuximab-related toxicity and visual analog scales, up to complete regression of the lesions in all treated areas (Gobbo et al., 2011). No adverse effects from treatment were reported. These findings suggest that LLLT may be an effective way of managing cetuximab- and radiation-induced skin toxicities. Herein we propose a pilot study to assess the efficacy of LLLT to mitigate and ameliorate the acneiform-rash, radiation dermatitis, and pain while assessing its impact on PR-QoL measures.

4.0 Study Endpoints

- 4.1 Primary Endpoint: The primary endpoint is to characterize the rate of any Grade 3 or higher Adverse Events as per CTCAE v4.0 (Common Terminology Criteria for Adverse Events).
- 4.2 Secondary Endpoints: Several patient reported QOL metrics will be collected as secondary endpoints.
 - quality of life data measured using the University of Washington Quality of Life Questionnaire (UW-QOL)
 - pain parameters assessed using Brief Pain Inventory (BPI)
 - dermatologic quality of life responses measured using the Dermatology Life Quality Index (DLQI)

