5.0 Study Intervention/Investigational Agent

THOR Laser system: MASCC/ISOO Clinical Practice Guidelines for mucositis (May 2014) recommend LLLT to prevent oral mucositis. In addition, the following studies have indicated that LLLT in the setting of RT alone or chemo-RT, appears to confer a benefit in reducing the rates of mucositis when compared to placebo or supportive care and is suggested for the prophylaxis of mucositis: -Phase III trial of low-level laser

therapy to prevent oral mucositis in head and neck cancer patients treated with concurrent chemoradiation. -Evaluation of low-level laser therapy in the prevention and treatment of radiation-induced mucositis: a double-blind randomized study in head and neck cancer patients. -Effect of low level helium-neon (He-Ne) laser therapy in the prevention & treatment of radiation induced mucositis in head & neck cancer patients. -Efficacy of He-Ne Laser in the prevention and treatment of radiotherapy-induced oral mucositis in oral cancer patients. -Low-energy He/Ne laser in the prevention of radiation-induced mucositis. A multicenter phase III randomized study in patients with head and neck cancer. Low level laser therapy for concurrent chemoradiotherapy induced oral mucositis in head and neck cancer patients - a triple blinded randomized controlled trial. -Oral mucositis prevention by low-level laser therapy in head-and-neck cancer patients undergoing concurrent chemoradiotherapy: a phase III randomized study. -Use of 660-nm diode laser in the prevention and treatment of human oral mucositis induced by radiotherapy and chemotherapy. -Efficacy of low-level laser therapy and aluminum hydroxide in patients with chemotherapy and radiotherapy-induced oral mucositis. -Laser phototherapy as topical prophylaxis against head and neck cancer radiotherapy-induced oral mucositis: comparison between low and high/low power lasers.

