6.2 Evaluation during Treatment

- Patients will be treated with the 69 diode LED cluster probe. The wavelength utilized are both 660 nm and 850 nm. The average power density is 100 mW/cm² and the spot size is 0.2 cm². Treatment time is 60 seconds to each site. There are a minimum of nine treatment sites: (1) left forehead, (2) right forehead, (3) left upper cheek/malar region, (4) right upper cheek/malar region, (5) right lower cheek / trigeminal nerve mandibular division distribution, (6) left lower cheek / trigeminal nerve mandibular division distribution, (7) submental region, (8) left neck, (9) right neck. Patients will be pretreated with a minimum of 3 sessions over 7 days before starting radiotherapy. Patients will receive LLLT at least twice the week prior to initiation of radiation and then at least three times per week during the course of radiation treatment.

- Adverse Event Assessment (Grading of skin toxicity and mucositis by patient)
- Completion of patient reported DLQI during treatment week 5 and at end of treatment

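### The hypothesis concerns grade III dermatitis, but no endpoint is the graded dermatitis rate, and the primary endpoint pools it with every other grade 3+ event

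*Combined protocol and SAP*

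**What the plan says.** The title and objectives are about mitigating radiation dermatitis. Section 2.2 gives the hypothesis: LLLT "will decrease the rate of grade III dermatitis".

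Section 4.1 defines the primary endpoint differently: "The primary endpoint is to characterize the rate of any Grade 3 or higher Adverse Events as per CTCAE v4.0". Sections 1.0, 14.1 and 14.2.1 repeat this, and 1.0 and 14.1 attach it to an aim of both safety and efficacy. The secondary endpoints are UW-QOL, BPI and DLQI.

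Section 14.2.1 plans a frequency, a percentage and an exact 95% CI for grade 3+ events, in enrolled patients with at least one dose. It adds a table of maximum grade by type of toxicity, and a summary of treatment-emergent events by organ class and/or preferred term. Section 12.1 plans a comparison with historical toxicity reports but names neither event nor benchmark. The only dermatitis figures are in Section 3.0: "The incidence of grade 3 radiation dermatitis was 18% with RT alone and 23% with RT with cetuximab".

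For skin assessment, Section 6.2 lists "Grading of skin toxicity and mucositis by patient" during treatment, Section 10.2 has treating physicians record toxicities weekly, and Section 6.3 schedules observer-reported skin reaction every three months after treatment.

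**The concern.** The event in the hypothesis is not an endpoint. Any grade 3+ adverse event is a sensible safety measure, but it counts dermatitis together with the significant mucositis that Section 10.2 expects and with everything else. DLQI has its own analysis and is skin-related, but it scores quality of life, not dermatitis grade.

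Two things are at stake. First, a change in the any-event rate cannot be read as an effect on dermatitis, because other events move the same rate. Mucositis is one candidate: Section 5.0 cites guidelines that "recommend LLLT to prevent oral mucositis". Second, if a dermatitis rate is extracted afterwards, its time window, source of grade and comparator would all be chosen with the data in view.

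**Working it through.** **1. The plan's own figures.** Inputs from Section 14.3: n = 75, exact (Clopper-Pearson) 95% CI. For 5, 10, 15, 20, 25 and 30 of 75 the intervals are 2.2–14.9, 6.6–23.2, 11.6–30.8, 17.1–38.1, 22.9–45.2 and 28.9–52.0%. All match the printed table after rounding. The maximum width is 23.6 points, at 38/75, which agrees with the stated 24%. The arithmetic is sound; the difficulty is which event it is applied to.

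**2. How much of a dermatitis effect the primary endpoint would show.** Let d be the grade 3+ dermatitis rate and q the rate of any other grade 3+ event. The documents do not give q, the overlap or an effect size, so all three are assumptions here. Under independence:

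any-event rate = 1 − (1 − d)(1 − q)

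For d = 0.20 and q = 0.50 this is 1 − 0.80 × 0.50 = 60%. With d halved to 0.10 it is 1 − 0.90 × 0.50 = 55%.

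| q | Any-event rate, d 20% → 10% | Fall (points) | Fall from d = 18% | Fall from d = 23% | Exact 95% CI width at the starting rate for d = 20% |
|---|---|---|---|---|---|
| 20% | 36% → 28% | 8 | 7.2 | 9.2 | 22.7 (27/75) |
| 50% | 60% → 55% | 5 | 4.5 | 5.75 | 23.1 (45/75) |
| 80% | 84% → 82% | 2 | 1.8 | 2.3 | 17.7 (63/75) |

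The 18% and 23% starting points are the Section 3.0 rates. Independence matters: from d = 20%, the fall is 0 points if every dermatitis case also has another grade 3+ event, and 10 points if none does.

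**3. The same change without any effect on dermatitis.** Hold d at 0.20 and lower q by 0.10. The any-event rate falls by (1 − 0.20) × 0.10 = 8 points at any q. The fall in q that mimics halving dermatitis is 0.10(1 − q)/0.80, that is 10, 6.25 or 2.5 points at q = 20%, 50% or 80%.

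**4. Whether the planned tables fill the gap.**
- The treatment-emergent summary in 14.2.1 is not limited to related events, so a dermatitis count could be taken from it. That requires tabulation by preferred term, which the and/or wording does not guarantee.
- The maximum-grade table covers toxicity, defined as events at least possibly related to study treatment. Dermatitis attributed to radiotherapy alone may drop out.
- Neither table carries a CI, window or comparator for dermatitis.

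**5. Who grades, and when.** The phrase in 6.2 can mean self-graded or recorded per patient. Section 10.2 points to physicians, and 6.3 to an observer, but only after treatment. Section 3.0 gives median dermatitis durations of 9.4 weeks (RT alone) and 11.1 weeks (with cetuximab). Both are shorter than 13 weeks, so at least half of such episodes starting during RT would be over by a visit 13 weeks after RT ends. The three-monthly observer assessments cannot be relied on for the worst grade.

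**6. What a named estimate would give at n = 75.** For example, 15/75 = 20.0% (11.6% to 30.8%) or 8/75 = 10.7% (4.7% to 19.9%), a 9.3-point difference. The intervals overlap, so even the right endpoint supports description only.

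**The case against.** The plan says it is descriptive and not for hypothesis testing, and any grade 3+ event is an ordinary phase I/II safety endpoint. The raw material probably exists: physicians record toxicities weekly, maximum grade is kept by type, Section 13.1 requires events to be followed until they resolve or stabilise, and Section 12.1 speaks of toxicity rates in the plural, which can be read as rates by type. On that view the gap is one of labelling.

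Three narrower points also have force. The dilution figures rest on assumed rates, and a single arm observes no fall. The mucositis evidence in Section 5.0 concerns LLLT given for oral mucositis, whereas the minimum sites in 6.2 are all external, so an effect of this treatment on mucositis is possible but not shown. Visits in 6.3 are at least three-monthly, so earlier ones are allowed, and the timing matters little if the weekly record supplies the grade.

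These points limit what can be claimed about size, and they show that the remedy is cheap. They do not remove the mismatch. A descriptive study still has to describe the event it is about, and the plan neither guarantees a dermatitis row that ignores attribution nor fixes its grader, window or interval.

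**Conclusion.** The concern holds and should be fixed. That no endpoint is the graded dermatitis rate, and that the primary endpoint pools dermatitis with all other grade 3+ events, follows from the text with no assumption. The size of the consequence is conditional: under independence, with other events at 20% to 80%, halving dermatitis from 18–23% would appear as a fall of between 9.2 and 1.8 points in the primary rate, and a change in other events alone could produce the same movement. Safety reporting is unaffected, and the interval calculations in 14.3 are correct.

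**What to change.** - In 1.0, 4.0, 14.1 and 14.2, name the per-patient rate of CTCAE grade 3+ radiation dermatitis, regardless of attribution to LLLT, as a co-primary or key secondary efficacy estimate with an exact 95% CI. Use the evaluable population already in 14.2.1. Keep any grade 3+ event as the safety endpoint.
- Take the worst clinician-assigned grade from the weekly physician record in 10.2, state the window (for example, first RT fraction to the first three-month visit), and reconcile the grader wording in 6.2 with 10.2 and 6.3.
- In 12.1, name the 18% and 23% rates as descriptive context only. Say that they are grade 3 rates, that 18% is for RT alone whereas 1.0 describes chemotherapy with concurrent RT, that the documents give neither their grading scale nor their window, and that a single arm cannot prove efficacy. Add no pass/fail rule. Rates by systemic agent are optional and would be imprecise.

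The cost is wording, with no new patients or visits; the weekly record may need an explicit skin grade. The 14.3 table applies unchanged if all 75 are evaluable. There is one side effect. Section 6.2 says "Patients will be pretreated with a minimum of 3 sessions over 7 days before starting radiotherapy", so the 14.2.1 population can include patients who never start RT. If 5 of 75 did not, 14 cases would read 14/75 = 18.7% rather than 14/70 = 20.0%. Reporting the number who never started RT is enough.

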5.0 Study Intervention/Investigational Agent

THOR Laser system: MASCC/ISOO Clinical Practice Guidelines for mucositis (May 2014) recommend LLLT to prevent oral mucositis. In addition, the following studies have indicated that LLLT in the setting of RT alone or chemo-RT, appears to confer a benefit in reducing the rates of mucositis when compared to placebo or supportive care and is suggested for the prophylaxis of mucositis: -Phase III trial of low-level laser

therapy to prevent oral mucositis in head and neck cancer patients treated with concurrent chemoradiation. -Evaluation of low-level laser therapy in the prevention and treatment of radiation-induced mucositis: a double-blind randomized study in head and neck cancer patients. -Effect of low level helium-neon (He-Ne) laser therapy in the prevention & treatment of radiation induced mucositis in head & neck cancer patients. -Efficacy of He-Ne Laser in the prevention and treatment of radiotherapy-induced oral mucositis in oral cancer patients. -Low-energy He/Ne laser in the prevention of radiation-induced mucositis. A multicenter phase III randomized study in patients with head and neck cancer. Low level laser therapy for concurrent chemoradiotherapy induced oral mucositis in head and neck cancer patients - a triple blinded randomized controlled trial. -Oral mucositis prevention by low-level laser therapy in head-and-neck cancer patients undergoing concurrent chemoradiotherapy: a phase III randomized study. -Use of 660-nm diode laser in the prevention and treatment of human oral mucositis induced by radiotherapy and chemotherapy. -Efficacy of low-level laser therapy and aluminum hydroxide in patients with chemotherapy and radiotherapy-induced oral mucositis. -Laser phototherapy as topical prophylaxis against head and neck cancer radiotherapy-induced oral mucositis: comparison between low and high/low power lasers.

6.0 Procedures Involved

6.1 Screening / Pre-treatment:

- Medical history
- Physical examination, including Karnofsky Performance Status and vital signs.
- Signed informed consent
- Subject body weight and height
- Quality of Life Assessments (UW QoL, BPI, DLQI)

6.2 Evaluation during Treatment

- Patients will be treated with the 69 diode LED cluster probe. The wavelength utilized are both 660 nm and 850 nm. The average power density is 100 mW/cm² and the spot size is 0.2 cm². Treatment time is 60 seconds to each site. There are a minimum of nine treatment sites: (1) left forehead, (2) right forehead, (3) left upper cheek/malar region, (4) right upper cheek/malar region, (5) right lower cheek / trigeminal nerve mandibular division distribution, (6) left lower cheek / trigeminal nerve mandibular division distribution, (7) submental region, (8) left neck, (9) right neck. Patients will be pretreated with a minimum of 3 sessions over 7 days before starting radiotherapy. Patients will receive LLLT at least twice the week prior to initiation of radiation and then at least three times per week during the course of radiation treatment.

- Adverse Event Assessment (Grading of skin toxicity and mucositis by patient)
- Completion of patient reported DLQI during treatment week 5 and at end of treatment

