6.3 Evaluation following Treatment

- Patients will be seen in follow-up at least every three months in the first year following completion of treatment.
 - Observer reported mucositis and skin reaction every three months for one year
 - Patient reported QoL assessments (UQ QoL, BPI, DLQI) every three months for one year

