10.0 Risks to Subjects

10.1 There are few risks associated with low-level laser therapy. This treatment is non-invasive and uses a cold laser output. Infrequently, eye damage has occurred with prolonged visual contact with the laser. Further, patients using concomitant supplemental niacin may experience, facial flushing.

10.2 Although no reported grade 3 or greater toxicities for LLLT have been published, patients will be closely monitored by a certified nurse prior to each delivery. Patients will be instructed to seek alternatives to niacin if taking this medication at the time of enrollment to the study. Additionally, eye protection is provided to all patients and staff present in the examination room during delivery of LLLT to prevent any eye damage. Significant mucositis from radiation is expected. Appropriate supportive care will be provided including analgesia, local therapies, and potentially low level laser therapy. Patients will be monitored weekly by the treating physicians to appropriately manage and record potential toxicities. Patients developing dermatologic adverse events will be monitored for the development of inflammatory or infectious sequelae. Supportive therapies other than the investigational intervention may include the following:

- Antibiotics: The benefit of routine antibiotics in uncomplicated (uninfected) rash is unclear. Some clinicians have used oral minocycline (Minocin), mupirocin (Bactroban), or topical clindamycin (Cleocin). Rash complicated by cellulitis should be treated with appropriate antibiotics based on clinical judgment or microbial sensitivity analysis.
- Antihistamines: Benadryl or Atarax may be helpful to control itching.
- Topical Steroids: The benefit of topical steroids is unclear.
- Retinoids: No data to support use. Use is not advised.

- Benzoyl peroxide: Should NOT be used--may aggravate rash.
- Makeup: Rash can be covered with makeup; this should not make it worse (use a dermatologist-approved cover-up, e.g., Dermablend, or any other type of foundation). Remove makeup with a skin-friendly liquid cleanser, e.g., Neutrogena, Dove, or Ivory
- Skin Cleansing Liqui-Gel.
- Moisturizers: Use emollients to prevent and alleviate the skin dryness, e.g., Neutrogena Norwegian Formula Hand Cream or Vaseline Intensive Care Advanced Healing Lotion.
- Sunlight: It is recommended that patients wear sunscreen and hats and limit sun exposure during treatment as sunlight can exacerbate any skin reactions that may occur.

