13.0 Provisions to Monitor the Data to Ensure the Safety of Subjects

13.1 Data will be monitored internally by the research manager. Any considerable deviations or concerns are to be addressed with the research manager and the principal investigator.

Expected adverse events from each intervention (radiotherapy and LLIT) are listed in the research protocol and are to be managed accordingly. For all adverse events, sufficient information should be obtained by the investigator to determine the causality, (i.e., study

drug or other illness). The investigator is required to assess causality and indicate that assessment on the CRF. Follow-up of the adverse event, after the date of therapy discontinuation, is required if the adverse event or its sequelae persist. Follow-up is required until the event or its sequelae resolve or stabilize at a level acceptable to the investigator. Adverse events that continue, or emerge within 30 days, after the patient's discontinuation or completion of the study will be followed until the events resolve, are considered stable, or can be ascribed to causes other than study treatment.

All serious AE meeting criteria for reporting will be reported per the University of Pittsburgh Institutional Review Board's policies. In the event of such adverse event, the investigator must report the event(s) via phone within 24 hours and a written report filed within 24 hours to the Principal Investigator.

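### The protocol does not settle whose grade of skin toxicity and mucositis during radiotherapy enters the CTCAE Grade 3 or higher primary endpoint

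*Combined protocol and SAP*

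**What the plan says.** The primary endpoint in Section 4.1 is to "characterize the rate of any Grade 3 or higher Adverse Events as per CTCAE v4.0". Section 14.2.1 reports it as a frequency and percentage with an exact 95% CI, and records for each patient the highest grade of each type of toxicity.

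Four places bear on who observes or grades toxicity:

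- Section 6.2, during treatment: "Adverse Event Assessment (Grading of skin toxicity and mucositis by patient". No scale, frequency or clinician grader is given.
- Section 6.3, after treatment: "Observer reported mucositis and skin reaction every three months for one year".
- Section 10.2, during treatment: "Patients will be monitored weekly by the treating physicians to appropriately manage and record potential toxicities". The same section says that "patients will be closely monitored by a certified nurse prior to each delivery".
- Section 13.1, for adverse events generally: "The investigator is required to assess causality and indicate that assessment on the CRF". It gives the investigator causality and does not mention the grade.

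Section 2.2 states the hypothesis that the laser "will decrease the rate of grade III dermatitis, a common finding seen in patients undergoing radiation therapy". Section 12.1 says the observed Grade 3 rates will be compared with published toxicity reports.

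**The concern.** The same two toxicities have one named assessor in Section 6.2 and another in Section 6.3. The pairing of *by patient* with observer reporting makes self-grading the natural reading of Section 6.2. Section 10.2 brings physicians in during treatment, but it speaks of recording, not grading, and names no form or endpoint source.

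Two sites, or two coordinators at one site, could therefore enter different grades for the same patient in the same week and both comply with the protocol. Under a maximum-grade rule, that choice can decide whether the patient counts as an event.

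The trial is single-arm and patients know that they receive the laser, so a self-grade can carry expectation, and no concurrent control group shares the error. The toxicities concerned also matter: dermatitis carries the hypothesis, and Section 10.2 expects significant mucositis.

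**Working it through.** **1. The plan's own figures.** Section 14.3 gives n = 75 and a maximum exact CI width of 24%. The Clopper–Pearson limits for x events are: lower = 2.5% quantile of Beta(x, n − x + 1); upper = 97.5% quantile of Beta(x + 1, n − x).

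| x/75 | Recomputed 95% CI | Section 14.3 |
|---|---|---|
| 5 | 2.2% to 14.9% | 2%, 15% |
| 10 | 6.6% to 23.2% | 7%, 23% |
| 15 | 11.7% to 30.8% | 12%, 31% |
| 20 | 17.1% to 38.1% | 17%, 38% |
| 25 | 22.9% to 45.2% | 23%, 45% |
| 30 | 28.9% to 52.0% | 29%, 52% |

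The widest interval is 23.6%, at x = 38, so the stated 24% holds. The width depends only on n and the count. The assessor question therefore leaves the sample size and stated precision unchanged; it concerns what the count measures.

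**2. The passages side by side.**

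| Section | Period | Who | Task | Is this grade named as endpoint source? |
|---|---|---|---|---|
| 6.2 | During treatment | Patient, as worded | Grading skin toxicity and mucositis | No |
| 10.2 | During treatment, weekly | Treating physicians | Managing and recording toxicities | No |
| 10.2 | Before each laser session | Certified nurse | Monitoring | No |
| 6.3 | Every three months for one year | Observer | Reporting mucositis and skin reaction | No |
| 13.1 | Any adverse event | Investigator | Causality on the CRF | No |
| 14.2.1 | Analysis | Not named | Maximum grade per toxicity type | No |

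No row supplies the missing rule. If *by patient* in Section 6.2 means per patient, that section names no grader at all, and the gap remains.

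**3. What the maximum rule does.** If self-grades replace physician grades, the count can move either way. If both are entered and the maximum is taken over them, the count cannot be lower than with physician grades alone. The direction thus depends on a choice the protocol has not made.

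**4. Illustration of size.** Sensitivity (Se) and specificity (Sp) of patient grading against physician grading are assumptions; the documents give neither. Observed rate = p × Se + (1 − p) × (1 − Sp), with p set to the two grade 3 dermatitis rates in Section 3.1: 18% (radiotherapy alone) and 23% (with cetuximab). Take Se from 0.6 to 1.0 and Sp from 0.90 to 1.0.

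- p = 23%, lowest (Se 0.6, Sp 1.0): 0.23 × 0.6 = 13.8%.
- p = 23%, highest (Se 1.0, Sp 0.90): 0.23 + 0.77 × 0.10 = 30.7%.
- p = 18%, lowest: 0.18 × 0.6 = 10.8%.
- p = 18%, highest: 0.18 + 0.82 × 0.10 = 26.2%.

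The historical rates differ by 23 − 18 = 5 points, so grading error of this assumed size could exceed that gap in either direction. The illustration is for dermatitis alone. The any-event endpoint could move less, because a patient with another Grade 3 event counts whoever grades the skin.

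**The case against.** The strongest reply is that clinicians are plainly present during treatment. Section 10.2 has weekly physician monitoring with recording of toxicities, and a nurse before each session. A reader might infer from Sections 6.2 and 6.3 alone that an observer sees the skin only every three months, or that the whole endpoint rests on the wrong assessor. Section 10.2 rules out the first inference. The second is not established: the source of the grade is unstated, and the endpoint covers any Grade 3 or higher event, whereas the Section 6.2 wording covers only skin toxicity and mucositis.

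A second reply is that *by patient* may be loose drafting for per patient. The next bullet in Section 6.2 uses the ordinary term for patient-reported data when it means the DLQI, and no self-grading instrument is named. That is a fair reading. It turns a wrong rule into a missing one, and does not remove the need for one.

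A third reply concerns consequences. A reader might infer that patient under-grading would make the interval exclude the 23% historical rate with no laser effect. The arithmetic does not support this. No effect against 23% means about 17/75; a 40% under-call leaves 17 × 0.6 ≈ 10/75, with CI 6.6% to 23.2%, which includes 23%. Starting from 15/75, a 20% under-call gives 12/75 (8.6% to 26.3%), which also includes it. A 40% under-call gives 9/75 (5.6% to 21.6%), which excludes 23% but still includes 18%; that start is already below 23%. The under-call fractions are assumptions, the historical rates are for dermatitis only, and Section 14.3 disclaims hypothesis testing.

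What survives all three replies is the unreconciled text and the unnamed source.

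**Conclusion.** The point holds as a gap in the definition of the primary endpoint. Sections 6.2, 6.3 and 10.2 are not reconciled, and Section 14.2.1 does not say whose grade enters the maximum-grade count. Taken literally, Section 6.2 permits unblinded self-grades to determine the skin and mucositis components.

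The size and direction of any bias cannot be computed from the documents. The ranges of about 14% to 31% (true 23%) and 11% to 26% (true 18%) rest wholly on assumed grading accuracy and show only that the issue could matter beside a 5-point historical gap. A change of assessor at the end of radiotherapy is possible but not certain, given the weekly physician recording, and no before-and-after comparison of grades is planned.

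The comparison with literature rates also assumes that those rates were graded by clinicians, which the protocol does not state. The correction is worth making before data are collected, because a self-grade cannot reliably be converted to a clinician's CTCAE grade afterwards.

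**What to change.** - **Section 6.2:** replace *by patient* with a CTCAE v4.0 grade for skin toxicity and mucositis assigned by the treating physician at each weekly on-treatment visit described in Section 10.2, and at end of treatment.
- **Section 14.2.1:** state that the maximum physician-assigned grade is the source for the primary endpoint.
- **Patient self-rating:** if wanted, keep it as a separate item, summarised descriptively and not entered into the maximum.
- **CRF:** add one field identifying the source of each grade.

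The cost is wording in two sections and one CRF field. The weekly physician monitoring is already planned, so no visits or staff are added and treatment is unchanged. The physician also knows that the laser is given, so the change makes the assessor consistent without blinding the assessment; that limit should be acknowledged when results are set beside historical rates.
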